7.1.1 Calculation of C_{max} , cC_{max} , t_{max} , and ct_{max}

The minimum requirement for the determination of the C_{max} and the cC_{max} is the inclusion of at least one quantifiable concentration within 1 hour post-exposure.

If C_{max} occurs at more than one time point, t_{max} will be assigned to the first occurrence of the C_{max} , similarly for cC_{max} .

7.1.2 Calculation of AUC

The minimum requirement for the calculation of the AUC is the inclusion of at least 3 plasma concentrations above the lower limit of quantification (LLOQ), with at least 1 of these concentrations following C_{max} .

$AUC_{(0-4h)}$ will be calculated using the linear trapezoidal method with the first value being C_0 and the last value being the last measurement performed at the 4h post T_0 timepoint.

If the 4h post T_0 timepoint is missing, the $AUC_{(0-4h)}$ will be set to missing. If the 4h post T_0 timepoint is collected between 3h and 3h30min post T_0 , the 4h post T_0 concentration will be extrapolated using the slope of all timepoints after t_{max} . If the 4h post T_0 timepoint is collected after 4h30 post T_0 , the 4h post T_0 concentration will be interpolated using the slope of all timepoints after t_{max} .

Similar rule will be applied for the calculation of $cAUC_{(0-4h)}$.

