7.1 Pharmacokinetic Parameters

For the calculation of PK parameters, the actual blood sampling times (collected in the CRF) rather than the nominal timepoints will be used in all calculations with the exception of the last collected sample prior to product use which can be considered as the T_0 value. Partial dates/times for PK assessments or T_0 will not in general be imputed.

For nicotine concentrations below the lower limit of quantification (BLOQ) :

- BLOQ values before T_0 will be imputed by LLOQ/2.
- BLOQ values after the last quantifiable value are not included in the analysis (e.g., for the calculation of AUC).
- Any BLOQ value (after T_0 and before the last quantifiable value) would need to be queried and, if confirmed, it will be imputed by LLOQ/2.

To minimize the carry-over effect in the plasma nicotine PK parameters due to limited washout periods, background-concentration correction will be applied to the nicotine concentration data.

Baseline nicotine concentration (C_0) will be defined as the last measured concentration prior to T_0 at Day 1 and at Day 30 (Visit 2 and Visit 6). The baseline correction will be implemented by calculating the PK parameters using adjusted concentration values as described below:

- Calculate the slope using a linear regression on the log concentration of the 3 pre- T_0 timepoints.
- If the slope is ≤ 0 , then use the slope to determine the elimination rate constant λ_z .

- If the slope is > 0 , then use the subject's slope that is ≤ 0 from the other visit to determine λ_z . If the subject's slopes are positive for the 2 visits, baseline corrected PK parameters will not be calculated.
- Adjust each concentration value post-baseline using the following formula:

$$cC_t = C_t - C_0 * e^{-\lambda_z t}.$$

cC_t is the corrected concentration at each time point, C_t is the concentration at each time point, C_0 is the pre-use baseline nicotine concentration at the given visit, λ_z is the elimination rate constant and t is the actual time.

If C_0 is BLOQ then there will be no baseline correction of the PK parameters. In that case cC_{max} , ct_{max} and $cAUC_{(0-4h)}$ will be considered as equal to C_{max} , t_{max} and $AUC_{(0-4h)}$, respectively.

- The following PK parameters will be derived from nicotine levels adjusted for baseline:

cC_{max}	Background-corrected maximum observed plasma concentration. cC_{max} will be reported as long as there is at least one quantifiable concentration post-exposure

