7.2 Pharmacodynamic effects

7.2.1 Visual Analogue Scale for Craving

A VAS-craving assessment will be used to assess the level of craving of the subject based on their response to the question, "How strong is your craving for cigarettes?" on a scale of 0 (no craving) to 10 (strong craving).

The VAS craving will be completed multiple times by the subject in relation to the P3P product used for PK assessment at Day 1 and Day 30. The first assessment will be done 10 minutes \pm 2 minutes prior to T_0 . Thereafter in relation to T_0 , the assessment is to be performed at 4 minutes \pm 2 minutes, at 10 minutes \pm 2 minutes, at 15 minutes \pm 2 minutes, 30 minutes \pm 5 minutes, 1 hour \pm 10 minutes, 2 hours \pm 10 minutes and 4 hours \pm 10 minutes. VAS will be assessed immediately after the collection of the time-matching PK samples.

For Day 1 and Day 30, baseline VAS-craving is defined as the measurement obtained at 10 \pm 2 min prior to the T_0 at Day 1 and Day 30, respectively.

Baseline for this endpoint is therefore different at Day 1 and Day 30.

VAS craving score and changes from baseline will be summarized by timepoint within Day 1 and Day 30. In addition, at Day 1 and Day 30, $AUC_{VAS(0-4)}$ will be derived using the linear trapezoidal method. For the calculations of $AUC_{VAS(0-4)}$, the actual timepoints of VAS

assessments instead of nominal timepoint will be used. The first VAS value to be taken into account in the derivation of $AUC_{(0-4)}$ is the value obtained 10 min prior to the T_0 timepoint, which will be considered as value at T_0 . The last value being the last measurement performed at the 4h post T_0 timepoint.

If the 4h post T_0 timepoint is missing, the $AUC_{VAS(0-4)}$ will be set to missing.

If the 4h post T_0 timepoint is collected after 3h but prior to 3h50 post T_0 , the 4h post T_0 the score will be derived using the extrapolation at 4h based on the last 2 timepoints collected prior to 4h.

If the 4h post T_0 timepoint is collected after 4h10 but prior to 5h post T_0 , the 4h post T_0 score will be interpolated between the last 2 timepoints.

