- d. Subjects with a BMI $< 18.5 \text{ kg/m}^2$ or BMI $\geq 32 \text{ kg/m}^2$ will be excluded. At V2 and V6 weight only will be recorded.
- e. Spirometry with and without bronchodilator performed at Screening. Spirometry without bronchodilator performed at the remaining visits. At Day -1, spirometry will be performed before and after product test. At Day 1 and Day 2 spirometry will be performed before product use and at the end of the daily product use.
- f. Only medication used for treatment of an AE/SAEs
- g. P3P product test using up to 6 P3P products (both P3P-1mg and P3P-2mg) will be conducted at Day -1 after enrollment. A wash-out period from any tobacco/nicotine containing products of at least 4 h prior to product test is needed.
- h. Sample taken in the morning prior to product use.
- i. Starting on the first day of each confinement period, subjects will abstain from tobacco/nicotine containing products for at least 10 h prior to P3P use for PK assessment on the second confinement day.
- j. Use of a single product with puffing depending on the subjects preference (*ad libitum* use) for a duration of up to 15 minutes.
- k. Each P3P used for PK assessment should be weighed prior to product use and within 1h after the end of the use.
- l. On Day 29 collection of unused P3P should occur right before the start of the 10h wash-out period.
- m. A total of 11 blood samples will be taken for PK parameter estimation at Day 1 and Day 30. Three blood samples will be taken prior to the start of product use (T_0) 1 hour \pm 5 minutes, 30 minutes \pm 5 minutes and 5 minutes \pm 2 minutes before T_0 . Thereafter in relation to T_0 , blood will be drawn at the following time points: after 4 minutes \pm 1 minute, after 7 minutes \pm 1 minute, after 10 minutes \pm 1 minute, after 15 minutes \pm 2 minutes, after 30 minutes \pm 2 minutes, after 1 hour \pm 5 minutes, after 2 hours \pm 5 minutes and after 4 hours \pm 5 minutes.
- n. NEQ, total NNAL and CEMA will be analyzed in spot urine and adjusted for creatinine.

Philip Morris Products S.A.

Protocol P3P-SE-02-RU

Statistical Analysis Plan

Draft v 1.0 / 17 July 2019

Confidential

Page 76 of 76

- o. Daily during the exposure period. Use of P3P and any other tobacco and nicotine containing products will be captured in a diary starting from Check-out of Day 1 until Discharge at Day 30.

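### SAP 7.1.2 leaves AUC(0-4h) and cAUC(0-4h) uncorrected when the last PK sample is drawn at 3h30–3h55 or 4h05–4h30, outside the ±5 min window

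*SAP*

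**What the plan says.** - **Times.** SAP 7.1 states that "the actual blood sampling times (collected in the CRF) rather than the nominal timepoints will be used in all calculations". The one exception is the last pre-use sample, which may stand as the T0 value.
- **End of the integral.** SAP 7.1.2 uses the linear trapezoidal method from C0, with "the last value being the last measurement performed at the 4h post" T0 timepoint.
- **Early sample.** The 4 h concentration is extrapolated on the post-tmax slope if the "timepoint is collected between 3h and 3h30min post" T0.
- **Late sample.** It is interpolated on the same slope if the "timepoint is collected after 4h30 post" T0.
- **Corrected AUC.** "Similar rule will be applied for the calculation of" cAUC(0-4h).
- **Missing sample.** If the 4 h sample is missing, AUC(0-4h) is set to missing.
- **Window.** SAP Table 11 and Appendix A (footnote m), and Protocol 4.1 and 7.4.1.1, all give 4 h ±5 min.
- **Status of a mistimed sample.** SAP Table 10 classes it as a minor deviation. SAP 10.4 removes subjects from the PK population only for major deviations. Protocol section 9 treats in-window timing as accepted variability.
- **Craving AUC, for comparison.** SAP 7.2.1 extrapolates when the "timepoint is collected after 3h but prior to 3h50 post" T0 and interpolates after 4h10. These are the edges of the ±10 min VAS window.

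**The concern.** The collection window ends 5 min either side of 4 h, but the correction starts only 30 min either side. In between, the sample is out of window, stays in the analysis, and closes the integral at its actual time. A last sample at 3h31 gives AUC(0-3.52h) and one at 4h29 gives AUC(0-4.48h). Both are reported as AUC(0-4h).

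The rule also creates a jump. A sample at 3h29 is extended to 4 h and one at 3h31 is not, and the same happens around 4h30. A sample drawn before 3h is neither missing nor covered by a rule.

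cAUC(0-4h) is one of the two parameters in the Day 30 ANCOVA and in the Day 30 versus Day 1 ANOVA of SAP 12.5.1, and the ANCOVA is repeated for uncorrected AUC. A mistimed last sample at one visit goes straight into that subject's Day 30:Day 1 ratio.

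**Working it through.** The documents give no figure to reproduce. The check compares the two sets of limits and then sizes the effect.

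**1. Limits side by side**

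| Actual time of the 4 h sample | In window? | What SAP 7.1.2 does |
|---|---|---|
| before 3h | no | no rule |
| 3h to 3h30 | no | extrapolates to 4 h |
| 3h30 to 3h55 | no | nothing; AUC ends early |
| 3h55 to 4h05 | yes | nothing; at most 5 min off |
| 4h05 to 4h30 | no | nothing; AUC ends late |
| after 4h30 | no | interpolates to 4 h |

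The uncorrected band is ±30 min, six times the window. For a flat profile, which bounds the error for any profile that does not rise at the end, this is 30/240 = 12.5% at the limits, against 5/240 = 2.1% at the window edges.

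**2. A case that can be followed by hand**

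Inputs: the SAP sampling times; half-life 1.35 h (Protocol 4.2). Assumed: linear rise to 1 at tmax = 0.25 h, one-phase decline, no residual nicotine. Then C(t) = 2^(−(t − 0.25)/1.35).

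- C(2) = 0.407, C(3.5) = 0.188, C(4) = 0.146, C(4.5) = 0.113.
- Trapezoids from 0 to 2 h: 0.009 + 0.018 + 0.028 + 0.069 + 0.235 + 0.390 + 0.544 = 1.294 (summed before rounding).
- Last sample at 4 h: 2.0 × (0.407 + 0.146)/2 = 0.553; total 1.847.
- Last sample at 3h30: 1.5 × (0.407 + 0.188)/2 = 0.447; total 1.740, or −5.8%.
- Last sample at 4h30: 2.5 × (0.407 + 0.113)/2 = 0.650; total 1.944, or +5.3%.

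Giving 40% of the peak to the 17 h phase (assumed) changes these to −9.3% and +9.0%.

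**3. Two-phase profile**

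Inputs: half-lives 1.35 h and 17 h (Protocol 4.2); input over 15 min, the maximum use time. Assumed: absorption rate 12/h; slow-phase weight 5% to 20%; for uncorrected AUC, residual nicotine of 50% to 100% of the peak increment.

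| Last sample | No residual (as for cAUC) | Uncorrected AUC, high residual |
|---|---|---|
| 3.51 h | −6.6% to −8.1% | about −9% to −10.1% |
| 4.49 h | +6.1% to +7.6% | about +8.5% to +9.8% |
| 3h55 or 4h05 | within ±1.7% | within ±1.7% |

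**4. One subject's Day 30:Day 1 ratio**

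Suppose one visit is sampled near 3h31 and the other near 4h29.

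- cAUC: 1.061/0.934 = 1.14 to 1.076/0.919 = 1.17.
- Uncorrected AUC, worst case: 1.098/0.899 = 1.22.

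**5. Group level**

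With about 30 subjects per arm, one such subject moves the arm's mean log ratio by about ln(1.17)/30 = 0.0052, or 0.5%, for cAUC. For uncorrected AUC it is ln(1.22)/30 = 0.0066, or 0.7%.

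**The case against.** The strongest reply is that little turns on this. Blood is drawn by staff on confined days to a set schedule, so a last sample 25 or more minutes off should be rare. One affected subject moves an arm's geometric mean by well under 1%. The study is descriptive, and SAP 12.1.6 says no claim rests on the intervals. Mistimed samples are also visible: SAP 12.2 summarises and lists deviations, SAP 12.5.1 lists actual collection times, and SAP 13.3 has a data review before lock. All of this stands, and it limits the weight of the point. It does not make the labelled interval right, and it leaves a known gap in a primary parameter to case-by-case judgement.

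Four stronger readings are tempting but not supported.

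- **A reader might infer that every sample from 3h30 to 4h30 gives a wrong AUC.** A sample at exactly 4 h is right, and Protocol section 9 accepts those at 3h55–4h05, where the error is under 2%.
- **A reader might take 22% as the error in the lead analysis.** It needs uncorrected AUC, high residual nicotine and opposite extreme mistimings at the two visits. SAP 12.5.1 refers to higher than expected T0 values, but that bears on the uncorrected AUC; background correction subtracts the residual from cAUC.
- **A reader might infer bias in the 2mg:1mg or Day 30:Day 1 ratio.** That requires timing to differ by arm or day, and nothing in the documents suggests it. Otherwise the effect is noise.
- **A reader might take the VAS rule as a complete model.** It too has no rule before 3h, and none from 5h on. The fair comparison is only that its correction starts at its own window edge.

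**Conclusion.** The point holds in a limited form. SAP 7.1.2 gives an AUC over the wrong interval for retained samples at 3h30–3h55 and 4h05–4h30, has a jump at 3h30 and 4h30, and has no rule before 3h. This follows from the text alone.

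The size depends on the assumed profile. Near the 30 min limits it is about 6% to 8% for cAUC (roughly 5% to 9% over the wider shapes tried) and up to about 10% for uncorrected AUC with high residual nicotine. One subject's Day 30:Day 1 ratio could shift by about 14% to 17% for cAUC if the two visits erred in opposite directions. Few subjects should be affected and the effect on group means is small. It is still worth changing, because the parameter is primary and the change is cheap.

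**What to change.** In SAP 7.1.2, replace the 3h30 and 4h30 triggers with the edges of the PK window, for both AUC(0-4h) and cAUC(0-4h):

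- sample from 3h to before 3h55: extrapolate the concentration to 4 h and integrate to exactly 4.0 h;
- sample after 4h05: interpolate the concentration at 4 h and integrate to exactly 4.0 h;
- sample before 3h: set the AUC to missing.

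The existing post-tmax slope method can stay. The largest uncorrected interval error then falls from 30 min to 5 min (12.5% to 2.1% of 4 h). Taking every profile to exactly 4.0 h would remove the mismatch and the threshold altogether.

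The cost is a sentence or two in the SAP and a few lines of code, with no new data. The downside is slightly more reliance on the fitted slope. SAP section 3 allows an amendment before database lock; after that, the change would be described in the research study report.

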7.1.3 Anomalous Values

If a concentration value is considered to be anomalous due to being inconsistent with the expected PK profile it will be flagged in the listings and will be reviewed for inclusion in the analysis during the pre-analysis data review.

Exclusion of abnormal concentrations (i.e. sudden increases or drops in concentration, inconsistent with a typical plasma nicotine PK profile) will be avoided, hence outlier values may only be excluded in the event there exists an explanation that clearly justifies such exclusion (e.g. protocol violation, documented sample handling errors, interruption of product use during fixed regimen, and/or analytical errors, best scientific judgment). The reason for the exclusion of abnormal concentrations (if any) will be documented.

7.2 Pharmacodynamic effects

7.2.1 Visual Analogue Scale for Craving

A VAS-craving assessment will be used to assess the level of craving of the subject based on their response to the question, "How strong is your craving for cigarettes?" on a scale of 0 (no craving) to 10 (strong craving).

The VAS craving will be completed multiple times by the subject in relation to the P3P product used for PK assessment at Day 1 and Day 30. The first assessment will be done 10 minutes \pm 2 minutes prior to T_0 . Thereafter in relation to T_0 , the assessment is to be performed at 4 minutes \pm 2 minutes, at 10 minutes \pm 2 minutes, at 15 minutes \pm 2 minutes, 30 minutes \pm 5 minutes, 1 hour \pm 10 minutes, 2 hours \pm 10 minutes and 4 hours \pm 10 minutes. VAS will be assessed immediately after the collection of the time-matching PK samples.

For Day 1 and Day 30, baseline VAS-craving is defined as the measurement obtained at 10 \pm 2 min prior to the T_0 at Day 1 and Day 30, respectively.

Baseline for this endpoint is therefore different at Day 1 and Day 30.

VAS craving score and changes from baseline will be summarized by timepoint within Day 1 and Day 30. In addition, at Day 1 and Day 30, $AUC_{VAS(0-4)}$ will be derived using the linear trapezoidal method. For the calculations of $AUC_{VAS(0-4)}$, the actual timepoints of VAS

assessments instead of nominal timepoint will be used. The first VAS value to be taken into account in the derivation of $AUC_{(0-4)}$ is the value obtained 10 min prior to the T_0 timepoint, which will be considered as value at T_0 . The last value being the last measurement performed at the 4h post T_0 timepoint.

If the 4h post T_0 timepoint is missing, the $AUC_{VAS(0-4)}$ will be set to missing.

If the 4h post T_0 timepoint is collected after 3h but prior to 3h50 post T_0 , the 4h post T_0 the score will be derived using the extrapolation at 4h based on the last 2 timepoints collected prior to 4h.

If the 4h post T_0 timepoint is collected after 4h10 but prior to 5h post T_0 , the 4h post T_0 score will be interpolated between the last 2 timepoints.

7.2.2 Sensory Questionnaire

A sensory questionnaire will be completed by each subject at Day 1 and Day 30 within 60 minutes after the P3P product use for PK assessment. The sensory questionnaire assesses the subject's opinion on the following sensory parameters:

- Puff information i.e., how they liked the puffs, harshness of puffs, and similarity to own brand;
- Strength of puffs on tongue, nose, mouth, windpipe, and chest.

Subjects will be asked to assess the 8 items of the questionnaire on a 7-point scale, ranging from "not at all" to "extremely" as presented in the table below.

Each item will be analysed individually, no total score will be computed.

Table 1: Sensory Questionnaire - Questions

Question	
1	How much did you like the puff you took?
2	How harsh were the puffs you took?
3	How similar to your own brand were the puffs?
4	Strength of puffs on tongue?
5	Strength of puffs in nose?
6	Strength of puffs in back of mouth & throat?
7	Strength of puffs in windpipe?

8

Strength of puffs in chest?

Reported values at Day 1 will be considered as baseline values.

7.2.3 ABOUT™-Product Experience

Product Experience will be assessed via a subject self-reported outcome measure at Day 1 and Day 30 within 60 minutes after the P3P product use for PK assessment, using the ABOUT™-Product Experience Questionnaire.

The questionnaire consists of three multi-item scales and two single-item scales.

The questionnaire assesses the degree to which subjects experience the reinforcing effects of P3P use by measuring:

- Product satisfaction (satisfying, tastes good, enjoy the product – Questions 1, 2, and 12).
- Psychological rewards (calms down, more awake, less irritable, helps concentrate, reduces hunger – Questions 4 to 8).
- Aversion (dizziness, nausea – Questions 9 and 10).
- Enjoyment of respiratory tract sensations (single-item assessment – Question 3).
- Craving reduction (single-item assessment – Question 11).

Subjects will be asked to assess the 12 items of the questionnaire on a 7-point scale, ranging from “not at all” to “extremely”.

The subscales scores will be derived by averaging the individual non-missing item scores if at least 50% are non-missing, otherwise the subscale score will be set to missing. Items are assessed on a 7-point scale, ranging from 1 (not at all) to 7 (extremely). Higher scores indicate greater intensity on that scale.

Reported values at Day 1 will be considered as baseline values.

7.3 Product acceptance and puffing/inhalation behavior

7.3.1 Product Acceptance Questionnaire

At Day 1 and Day 30, subjects will complete the product Acceptance Questionnaire. This questionnaire will be used to assess product characteristics of P3P relevant to determine subjects' acceptability of the product. Subjects will be asked to rate P3P in terms of sensory attributes, ease of use and occasions of use.

A baseline version of the product acceptance questionnaire consisting of 5 questions will be answered at Day 1, while a 6-questions version containing an additional question asking about occasions of P3P use will be answered at Day 30.

Answers to questions 1 to 4 will be considered continuous while answers to questions 5 and 6 will be presented using frequencies.

Reported values at Day 1 will be considered as baseline values.

Table 2: Product Acceptance - Questions

Question	Answer
1. What is your overall opinion about P3P	I dont like it at all =1, 2, 3, 4, 5, 6 to 7 = I like it very much
2. a. What is your opinion on P3P's taste intensity?	Not intense at all =1, 2, 3, 4, 5, 6 to 7 = Very intense
2. b. What is your opinion on P3P's aftertaste intensity?	Same as above
2. c. What is your opinion on P3P's cooling intensity?	Same as above
2. d. What is your opinion on P3P's visibility of exhale?	I dont like it at all =1, 2, 3, 4, 5, 6 to 7 = I like it very much
2. e. What is your opinion on P3P's acoustic feedback(sound)?	Same as above
2. f. What is your opinion on P3P's tactile feedback (vibration)?	Same as above
2. g. What is your opinion on P3P's having no electronics/need no charging?	Same as above
2. h. What is your opinion on P3P's length of experience?	Same as above
2. i. What is your opinion on P3P's consistency of sensation between puffs?	Not intense at all =1, 2, 3, 4, 5, 6 to 7 = Very intense
3. a. Please indicate how easy you consider piercing the capsule to be?	Not easy at all =1, 2, 3, 4, 5, 6 to 7 =Very easy
3. b. Please indicate how easy you consider understanding when P3P is activated to be?	Same as above
3. c. Please indicate how easy you consider drawing on P3P to be?	Same as above
3. d. Please indicate how easy you consider inhaling to be?	Same as above
3. e. Please indicate how easy you consider understanding the end of P3P use to be?	Same as above
4. a. What is your opinion on P3P when you compare it to pipe?	I like P3P much less = 1, 2, 3, 4, 5, 6 to 7 = I like P3P much better (I did not use this = missing)
4. b. What is your opinion on P3P when you compare it to Hookah?	Same as above
4. c. What is your opinion on P3P when you compare it to Heat-not-burn tobacco?	Same as above
4. d. What is your opinion on P3P when you compare it to e-cigarette?	Same as above
4. e. What is your opinion on P3P when you compare it to Snuff or chewing tobacco?	Same as above
4. f. What is your opinion on P3P when you compare it to Nicotine Replacement Therapy (e.g. patches, gum) ?	Same as above
5. After consuming one P3P, which statement best describes how you feel?	I feel satisfied

6. What are three occasions on which you were using P3P the most during the last month?

- I do not feel satisfied and want to use another P3P again shortly afterwards
- I do not feel satisfied and want to consume one of my regular cigarettes shortly afterwards
- At home, indoors
- At home, outdoors (e.g. garden, balcony)
- In areas where I don't normally smoke (e.g. at my desk at place of work)
- In a designated outdoor smoking area at my place of work
- In a designated indoor smoking area at my place of work
- In a designated indoor or outdoor smoking area (e.g. terrace) in a bar, restaurant, cafe or nightclub
- In public areas (e.g. in the street, in a park)
- At a friend or colleague's home
- At a family member's home
- In the car

